Risks and solutions envisaged for task 2.6: Risk: data loss. Contingency: In order to ensure no data loss, a periodical back up will be carried out.

WP3.- Probiotic effects on AD dementia

The objective of this WP is to enhance the knowledge of the potential positive probiotic effects in the gut composition and on their clinical symptoms of the Alzheimer disease patients. In this sense our group has already done studies of the beneficial effects of the PNU-282987, an alpha 7 nicotinic receptor agonist in an animal model of Alzheimer's disease, with positive results in anxiety symptoms but not in cognitive (Vicens et al, 2013a, 2013b, 2017).

It is generally agreed that probiotic strains should be of host origin with a beneficial effect on the host, withstand into food stuff with a high count of them, withstand transits through intestine and colonize lumen of the tract, produce antimicrobial agents, and be technologically appropriate for industrial production (Shewale et al., 2014). Due to the lack of evidence about the appropriate dosage of probiotics for AD, we used the below-mentioned doses based on few previous studies in healthy subjects (Benton et al., 2007; Mohammadi et al., 2015) and on AD patients with positive results (Akbari et al 2016).

To achieve this objective, the following tasks will be carried out in this WP:

Task 3.1. Patients recruitment and assignment to experimental groups

We will recruit a total of 60 AD patients, 30 will ingest the probiotic mixture and 30 will ingest placebo (randomized assignment to the groups will be done). The experimental group will take the probiotic ingest daily: *Lactobacillus acidophilus*, *Lactobacillus casei*, *Bifidobacterium bifidum*, and *Lactobacillus fermentum* (2×10^9 CFU/g of each). This mixture of bacteria has been showed to have positive results with 12 weeks treatment (Akbari et al, 2016). The duration of the treatment will be 24 weeks, with two posttreatment assessment, at 12 weeks and at 24 weeks.

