To calculate sample size, we used the standard formula suggested for clinical trials by considering type one error(a) of 0.05 and type two error(b) of 0.20 (power = 80%) based on a previous study (Akbari et al, 2016). We used 1.3 as SD and 1.1 as the difference in mean (d) of MMSE as key variable. Accordingly, we needed 25 persons in each group. Assuming 5 dropouts in each group, the final sample size was determined to be 30 persons per group. This sample size is enough to detect differences in cognitive performance due to a probiotic treatment (Akbari et al, 2016).

The criteria for the recruitment will be: Inclusion criteria: AD diagnosed by the neurology service; more than 65 years. Exclusion criteria: Comorbidity with other significant neurology disease, infectious treatment with antibiotics in the previous 6 months prior to providing the stool sample, corticosteroid use, immunosuppressors or immunostimulants treatment, illnesses of the GI tract, large doses of commercial probiotics consumed (greater than or equal to 10^8 cfu per organisms per day).

The hospitals will have publicity of the study and when target patients were attended by the neurologists/neuropsychologist (group research members) will be informed of the study and encourage enrolling. Also, neuropsychologists of the Alzheimer's Association will inform of the study and encourage enrolling. In the Alzheimer stimulation center of Alzheimer Association come regularly about 60-70 patients. If the patients agree to enroll the study, they (or legal tutor) will sign the informed consent and give their contact telephone number to be able to be contacted again. The neurologists/neuropsychologist also will give them the stool collection pack, to be kept for them until the contact of the research team for the interview.

Risks and solutions envisaged for task 3.1: Risk: patient lost from the recruitment until the interview, fail in neuropsychological assessment, fecal collection or treatment adherence. Contingency: we will recruit some more patients of each group 5-10 patients.

Task 3.2. Citation of the volunteers before the probiotic intake period: assessment, stool sample collection and treatment initiation

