There will be two assessments after 12-week treatment period and 24-week treatment period. At the time of the interview, the volunteer will come accompanied and give the stool sample in the saving tube of the collection kit. The assessment will be the same that in task 3.2.

The researcher will give to the volunteer in the 12-week meeting the treatment to take from the day after the interview until 12 weeks after and a new stool collection kit (in order to bring another stool sample, the next interview day, after 12 weeks).

Task 3.4. Stool samples saving

Same as task 2.4.

Task 3.5. Stool samples shipment to laboratory analysis

Same as task 2.5.

Task 3.6. Obtainment of the data and statistical analysis

The fecal samples will be analyzed by Sequencing Technics and characterize their bacterial taxonomic composition. These data will be received within 2-3 months after the samples reach the analyzer laboratory.

Statistical analysis with microbiota data and all other data collected will be done. All the descriptive for all the data collected will be calculated for each group. Microbiota data from experimental groups and the results of the assessments will be compared (Student's t-test and Pearson Chi-square test). Multivariable logistic regression analyses will be done to relate microbiota composition and results of the neuropsychological assessment.

At the moment of statistical analysis will be ask a methodology specialist to revise them and decide if any other analysis could be interesting to do.

Risks and solutions envisaged for task 3.6: Risk: data loss. Contingency: In order to ensure no data loss, a periodical back-up will be carried out.

WP 4.- Dissemination and formation

This WP aims to effectively disseminate our results in international conferences, publishing the results in international scientific journals of high impact factor (1Q-2Q) and disseminate to the benefit society directly as well as educate of the benefits of the variables studied and resulted positive, e.g. the Mediterranean lifestyle, probiotic consumption etc. To achieve this objective, the following tasks will be carried out in this WP:

Task 4.1. Attendance and presentation of communications to congresses

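### WP3 expects 5 of 30 dropouts per arm but plans only a t-test on patients observed at the visit, so MMSE-related loss that differs between arms can bias the comparison

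*Combined protocol and SAP*

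**What the plan says.** All references are to WP3 of the combined protocol and SAP.

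- **Sample size (Task 3.1).** The MMSE is the design variable: "We used 1.3 as SD and 1.1 as the difference in mean (d) of MMSE as key variable". From these inputs the plan derives a requirement of 25 evaluable patients per arm and then adds an allowance for loss: "Assuming 5 dropouts in each group, the final sample size was determined to be 30 persons per group".
- **Other provision for loss (Task 3.1, risks).** The foreseen losses include patients who never reach the interview, failed neuropsychological assessment, failed stool collection and poor adherence. The only remedy is to recruit 5-10 more patients per group.
- **Visits (Tasks 3.1 to 3.3).** Treatment lasts 24 weeks, "with two posttreatment assessment, at 12 weeks and at 24 weeks". Task 3.2 includes the MMSE before treatment, and Task 3.3 states for the later visits: "The assessment will be the same that in task 3.2". MMSE is therefore scheduled at baseline, week 12 and week 24.
- **Analysis (Task 3.6).** "Microbiota data from experimental groups and the results of the assessments will be compared (Student's t-test and Pearson Chi-square test"). The logistic regression that follows relates microbiota to test results and is not a comparison of arms on MMSE. No deciding visit, analysis population, missing-data method or sensitivity analysis is given. The data-loss contingency there is a file back-up. A methodology specialist may add analyses once the statistical work is under way.

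**The concern.** The plan expects to lose one patient in six per arm and answers this only with numbers. Replacing lost patients restores precision. It does not make those who remain comparable between arms if the reason for leaving is tied to cognition and operates differently under probiotic and placebo. In a progressive disease followed for 24 weeks, such loss is plausible.

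The trial will already hold information on many of those patients, namely a baseline MMSE and, for anyone lost after week 12, a week-12 MMSE. The stated t-test cannot use either for a patient who is absent at the visit tested. At stake is the between-arm MMSE difference, the variable on which the trial was sized.

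**Working it through.** **Step 1: the plan's own figure.** Inputs from Task 3.1: difference 1.1, SD 1.3, alpha 0.05, power 80%. Sidedness is not stated, so two-sided is assumed.

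n per arm = 2 × (1.960 + 0.842)² × (1.3/1.1)² = 21.9, so 22 by the normal approximation.

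The two-sided t-test needs 23 (power 80.1%). At 25 per arm its power is 83.4%, so the stated 25 is reproduced with a small margin. 25 + 5 = 30, a loss of 5/30 = 16.7% per arm. If loss is random, power is adequate.

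**Step 2: what selection does to the mean.** If a fraction p of an arm is lost,

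mean of those retained − mean of the whole arm = p × (mean retained − mean lost).

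The bias in the arm difference is this quantity in one arm minus the same quantity in the other. With p = 1/6 and a retained-minus-lost gap of 1.1 points in one arm only, bias = 1.1/6 = 0.18 points. If the gap is the same in both arms, bias = 0.

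Extreme case: one arm loses exactly its lowest sixth and the other loses at random. For a normal score the retained mean rises by φ(0.967)/(5/6) = 0.250/0.833 = 0.30 SD, and 0.30 × 1.3 = 0.39 points. That is 0.39/1.1 = 35% of the design difference.

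**Step 3: simulation of the t-test against a likelihood estimate that also uses baseline and week-12 MMSE.** From the plan: 30 per arm, SD 1.3, 1/6 lost per arm. Assumed: correlation between visits 0.5 to 0.7, the loss mechanism, and the share of loss falling after week 12 (none, half or all). There were 2,500 trials per scenario. The table shows results with no true effect.

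| Loss pattern | t-test bias (points) | t-test type I error | Likelihood bias |
|---|---|---|---|
| Random | within 0.02 of 0 | 4.5-5.8% | within 0.02 of 0 |
| Low earlier scorers lost, equally in both arms | within 0.02 of 0 | 4.4-5.1% | within 0.02 of 0 |
| Low earlier scorers lost, one arm only | 0.13-0.20 | 5.7-8.3% | within 0.02 of 0 |
| Opposite selection in the two arms | 0.26-0.39 | 11-20% | within 0.02 of 0 |
| One arm, loss driven by the unseen week-24 score | 0.27-0.29 | 11-13% | 0.13-0.23 |

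Monte Carlo error for a 5% rate is √(0.05 × 0.95/2500) = 0.4 percentage points, so the low end of the one-arm type I range is only slightly above nominal. With a true effect of 1.1 and random loss, t-test power was about 84%.

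**Step 4: a second simulation**, with 10 of 60 lost after week 12 and noisy selection on the week-12 score.

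- Selection in one arm only, 5 against 5: false gain 0.14-0.20, rejection 7-9%.
- True difference 1.1, one dropout rule common to both arms: the t-test estimated 0.97-1.01 with power 77%. Placebo patients score lower, so they leave more often, and the counts move away from the planned 5 and 5.
- In both settings the likelihood estimate was within about 0.01 of the truth and type I error was held at 5%.

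**The case against.** The strongest reply is that the plan contains no rule to exclude anyone. It is silent on visit, population and missing data, and it brings in a specialist. That is fair as to wording: exclusion is an inference from the method. But a t-test on a visit's score, or on change to that visit, cannot include a patient not seen there, and no imputation is planned. Choosing the missing-data method when the data are already in hand would let the results influence it.

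Four stronger readings are tempting, and the documents do not support them.

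- *Most dropouts could be kept through their week-12 score.* No section says when the 5 leave. Task 3.1 counts loss before the interview, where no MMSE may exist, while failed stool collection or poor adherence need not lose the MMSE at all. The week-12 score helps only a week-24 comparison. No deciding visit is named, and Task 3.2 still describes a 12-week trial.
- *The MMSE result is biased.* It can be. The bias needs loss that is related to MMSE and differs between arms, and its direction cannot be known from the documents.
- *The bias is large.* The upper figures need opposite or near-deterministic selection, or loss more unequal than the planned 5 and 5.
- *A repeated-measures model cures the problem.* It is unbiased in Steps 3 and 4 where loss was made to depend on scores it sees. Where loss depended on the unseen week-24 score, roughly half or more of the bias remained.

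**Conclusion.** The concern holds in a limited form. WP3 plans for one-sixth loss per arm and names, as its only between-arm method for MMSE, a test that cannot use the earlier scores of absent patients. Extra recruitment covers power only. With about 5 lost per arm and selection in one arm, the false difference is about 0.13-0.20 points, or 12-18% of the 1.1-point design difference (0.13/1.1 and 0.20/1.1), with type I error of about 6-9%. With random or equally selective loss it is about zero.

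These sizes rest on assumed dropout mechanisms and on visit correlations of 0.5-0.7, since timing and reasons of dropout are not documented. The case for changing the analysis does not depend on the exact size. A better method is available on data already scheduled, and under random loss it performs about as well as the t-test.

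**What to change.** In Task 3.6:

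1. Name the deciding visit.
2. Make the MMSE comparison a repeated-measures model on all randomised patients with any MMSE, with arm, visit, arm-by-visit and unstructured covariance. Include baseline MMSE as a first repeated measure or as a covariate; the first form also keeps patients whose only score is baseline. Read the arm contrast at the deciding visit.
3. Keep the completer t-test as a secondary analysis.
4. Add a sensitivity analysis for loss that depends on unobserved scores, for example delta-adjusted imputation.
5. Report losses by arm, visit and reason.

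The cost is SAP wording and a little more analysis work, with no new patients or measurements. The limitation to state is that the model removes only the bias that observed scores predict, which is why item 4 is needed.

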Volunteers were contacted and cited for an interview (at the same hospital, center Alzheimer's Association or at home, the more comfortable to them). In order to obtain the stool sample, the researcher will explain the instructions (a paper with the written instructions will be with the kit too) and encourage to collect 1-2 days before the interview and keep in the freeze until they deliver us in the interview (stool collection and preservation system, Norgen, Biotek Corporation, Canada).

At the time of the interview, the volunteer will come accompanied and give the stool sample in the saving tube of the collection kit.

The assessment will include:

-Patient identification, sex, age, level of education, years of schooling, weight and height and diagnostic (others sociodemographic data) and revision of the inclusion/exclusion criteria

-Medication, diseases (diabetes, cholesterol, hypertension, etc)

-Tests/scales:

-Mediterranean lifestyle index interview (MEDLIFE), (Sotos-Prieto, et al, 2015), MEDLIFE will give us information about how the patient follow Mediterranean diet and habits;

-Live Events Questionnaire-Cuestionario de sucesos vitales (CSV), (Sandín & Chorot, 2017), CSV the information about successful stress events that could affect and modify the main relations of the study

-Screening cognitive tests/scales: Mini Mental State Examination (MMSE) (Folstein et al, 1975), Global Deterioration Scale-Functional Assessment Staging (GDS-FAST) (Reisberg, 1982, 1988), Clinical Dementia Rating (CDR) (Hughes, 1982)

-Cognitive Reserve scale (León-Estrada et al, 2017)

-Activities of Daily Living (ADLs) and Neuropsychiatric scale (Test Barcelona-2), (Peña-Casanova, 2019)

-Anxiety and Depression Scale (Goldberg et al 1988)

-Test Barcelona-2 battery, beta abbreviated version (Peña-Casanova, 2019), we will use Test Barcelona-2 battery to an extensive and deep neuropsychology assessment.

The patients were requested not to change their ordinary physical activity and not to take any nutritional supplements during the 12-week trial. The researcher will give to the volunteer in this meeting the treatment to take from the day after the interview until 12 weeks after and a new stool collection kit (in order to bring another stool sample, the next interview day, after 12 weeks).

Task 3.3. Citation of the volunteers after the probiotic intake period: assessment and stool sample collection

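### Task 3.6 names only a t-test and Pearson chi-square, without saying which applies to which variable or on what scale abundances are compared; two natural readings lose substantial power.

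*Combined protocol and SAP*

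**What the plan says.** The stated aim of WP3 is to "enhance the knowledge of the potential positive probiotic effects in the gut composition and on their clinical symptoms" of patients with Alzheimer disease, so gut composition stands beside clinical symptoms as an objective.

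On the data, Task 3.6 says: "The fecal samples will be analyzed by Sequencing Technics and characterize their bacterial taxonomic composition". On the comparison of arms it says: "Microbiota data from experimental groups and the results of the assessments will be compared (Student's t-test and Pearson Chi-square test"). These are the only two tests named for comparing arms. The section does not say which test goes with which variable. It gives no transformation, diversity measure, community-level test, rank test or ordinal model.

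One further model is planned: "Multivariable logistic regression analyses will be done to relate microbiota composition and results of the neuropsychological assessment". It relates microbiota to test results and is not described as a comparison of probiotic with placebo. Task 3.6 ends by leaving it to a methodology specialist, at the time of analysis, to decide on any further analyses.

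CDR and GDS-FAST are in the Task 3.2 assessment list. Task 3.3 repeats that assessment, and the stool sample, after 12 and 24 weeks. Task 3.1 bases the sample size on MMSE alone.

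**The concern.** Relative abundances from sequencing are shares of a total. They are typically right-skewed and often zero. On the untransformed scale, with about 25 patients per arm, a few high values inflate the variance and can hide a real shift.

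Shares are also tied to one another. Suppose an ingested genus has share p, triples in absolute amount, and nothing else changes. Every other share is then multiplied by 1/(1 + 2p). All the other taxa appear to fall although none has. A difference in raw shares therefore cannot be read as a real fall in those taxa.

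CDR and GDS-FAST are ordered stages. Pearson chi-square treats the stages as unordered and spreads the signal over several degrees of freedom, with small expected counts at this sample size.

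At stake is the chance of detecting an effect on gut composition and on staging, and the interpretation of any taxon that appears to fall.

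**Working it through.** **Step 1. The plan's own figure.** Inputs from Task 3.1: SD 1.3, MMSE difference 1.1, alpha 0.05 (two-sided assumed), power 80%.

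- Normal approximation: n = 2(1.960 + 0.842)² × 1.3²/1.1² = 21.9, so 22 per arm. The t-distribution gives 22.9, so 23.
- The stated 25 is slightly conservative. Power for that difference is 83% at 25 per arm and 90% at 30.
- Dropout: 25/(1 − 5/30) = 30, as stated.

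A t-test suits MMSE, so this point leaves the sample size untouched.

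**Step 2. Abundance of a single taxon.** The documents give no variance, prevalence or effect size for any taxon, so what follows is assumed: log-normal abundances, a 3-fold shift, 25 per arm, two-sided 0.05, and zeros equally frequent in both arms. Simulated power:

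| Zeros | Log-SD | t-test, raw | t-test, log | Rank test |
|---|---|---|---|---|
| none | 1.5 | 37% | 71% | 68% |
| none | 2.0 | 13% | 48% | 45% |
| 20% | 1.5 | 26% | 29% | 33% |
| 20% | 1.0 | 69% | 50% | 61% |
| 40% | 1.0 | 47% | 27% | 25% |

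Check without simulation: on the log scale the standardised shift is ln 3/1.5 = 0.732 or ln 3/2.0 = 0.549. The two-sample t-test then has exact power 72% and 48%, which agrees with the first two rows.

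A second set fixed the shift at 0.8 log-SD, that is exp(0.8) = 2.2-fold, exp(1.2) = 3.3-fold and exp(1.6) = 5.0-fold at log-SD 1, 1.5 and 2. With no zeros, power was 62%, 42% and 28% for the raw t-test, against 79%, 79% and 78% on the log scale and 77%, 77% and 76% for the rank test. With 30% zeros on placebo and half as many on probiotic, the raw t-test had 62%, 43% and 28% and the rank test 72%, 73% and 71%. The gap persists here because the zeros themselves differ between arms, unlike in the table. The size of the loss thus depends on how zeros arise.

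With no true shift, the raw t-test rejected in about 2% to 4% of runs. The problem is efficiency, not false positives.

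**Step 3. Staging scales.** Assumed stage probabilities on placebo: CDR 0.20/0.45/0.25/0.10 at 0.5, 1, 2 and 3; GDS-FAST 0.10/0.30/0.30/0.20/0.10 over five stages. A proportional odds ratio was applied, with 25 per arm:

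| Scale | Odds ratio | Chi-square | t-test | Rank test | Rank minus chi-square |
|---|---|---|---|---|---|
| CDR | 3 | 34.8% | 48.3% | 53.0% | 18.2 |
| CDR | 4 | 54.0% | 66.9% | 73.3% | 19.3 |
| CDR | 5 | 68.0% | 78.2% | 84.4% | 16.4 |
| GDS-FAST | 3 | 32.6% | 55.8% | 56.2% | 23.6 |
| GDS-FAST | 4 | 47.5% | 73.8% | 74.7% | 27.2 |
| GDS-FAST | 5 | 65.4% | 85.1% | 86.2% | 20.8 |

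Chi-square costs 16 to 27 points. The t-test costs 5 to 6 points on CDR and about 1 point or less on GDS-FAST. A different 5-level distribution (0.10/0.25/0.35/0.20/0.10, odds ratio 3) gave chi-square 33%, t-test 56% and rank test 56%. In 91% of those runs more than a fifth of the expected counts were below 5.

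All power figures are at an unadjusted 0.05. Adjustment across taxa would lower those in step 2.

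**The case against.** The strongest reply is that the plan does not say what the concern needs it to say. Task 3.6 lists two tests jointly and ties neither to a variable. A t-test on log abundance or on a diversity index would fit its wording, and so would a t-test on GDS-FAST, which loses almost nothing. This stands. A reader might infer that the plan commits to raw-scale t-tests and to chi-square for CDR and GDS-FAST; the documents do not support that, and both losses are conditional.

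A second reply is that neither test is wrong in itself. This also stands. A t-test compares patients, who are independent. The closure of shares affects what a difference means, not the validity of a randomised comparison of one share. Chi-square is a proper test for presence or absence of a taxon. With zeros and low skew, the raw t-test can be the most powerful of the three.

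A third reply is that the methodology specialist will settle the matter. This does not stand. The clause names no method and takes effect only at the time of analysis, so a choice made under it is not prespecified. The logistic regression does not help either, because it is not planned as a comparison of arms.

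**Conclusion.** The concern holds as an under-specified and improvable analysis. Task 3.6 gives neither a mapping of tests to variables nor a scale for abundances, and the two readings that its wording most readily invites are inefficient.

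Under the assumed log-normal model without zeros and a 3-fold shift, raw-scale t-tests fall about 34 to 35 points short of the log scale (37% v 71%, 13% v 48%). With 20-40% zeros, equally frequent in both arms, the gain shrinks or reverses. Chi-square on the staging scales falls about 16 to 27 points short of a rank test under the assumed distributions.

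It would go too far to conclude that the named tests suit none of the data, or that the trial's results would be invalid. Type I error for a single taxon is not inflated, the t-test fits MMSE, and the sample size is unaffected. The direction of the losses for prevalent, skewed taxa and for chi-square on ordered stages is well founded. Their size depends on distributions that the documents do not give.

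**What to change.** Rewrite Task 3.6 so that each variable has a named method:

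1. **Community composition:** one prespecified comparison of arms on a log-ratio distance, for example PERMANOVA.
2. **Prevalent taxa:** centred-log-ratio abundances compared between arms with the baseline value as covariate, and false-discovery-rate control across taxa. State the prevalence cut-off in advance.
3. **Sparse taxa:** presence or absence, by chi-square or an exact test.
4. **CDR and GDS-FAST:** a proportional-odds or rank-based analysis that uses baseline, in place of Pearson chi-square.
5. **MMSE and other continuous scores:** keep t-type or ANCOVA methods.

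The baseline stool sample and assessments are already collected under Task 3.2, so no extra patients, visits or samples are needed. The cost is SAP wording and routine software. The downside is that log-ratio effects are harder to explain to clinical readers, and no method is best for very sparse taxa.

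### Task 3.6 plans logistic regression without naming a binary outcome or cut-point, and compares microbiota between arms without multiplicity control

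*Combined protocol and SAP*

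**What the plan says.** The WP3 analysis is one short paragraph in Task 3.6 of the combined protocol and SAP.

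- **Laboratory data:** "The fecal samples will be analyzed by Sequencing Technics and characterize their bacterial taxonomic composition". No taxonomic level, list of taxa or summary index is given.
- **Arm comparison:** "Microbiota data from experimental groups and the results of the assessments will be compared (Student's t-test and Pearson Chi-square test". No error-rate control is stated, and the parallel WP2 analysis (Task 2.6) has none to borrow.
- **Association model:** "Multivariable logistic regression analyses will be done to relate microbiota composition and results of the neuropsychological assessment". The dependent variable, any cut-point, the covariates and the visit are all left open.
- **Visits (Task 3.3):** "There will be two assessments after 12-week treatment period and 24-week treatment period", each with a stool sample. Whether one or both are tested is not stated.

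The neuropsychological results are mainly scores. The Task 3.2 list includes "Screening cognitive tests/scales: Mini Mental State Examination (MMSE", the staged scales GDS-FAST and CDR, and the Test Barcelona-2 battery. The Task 3.1 sample size handles the main score as a mean with a standard deviation: "We used 1.3 as SD and 1.1 as the difference in mean (d) of MMSE as key variable". Task 3.2 also collects stressful life events because they "could affect and modify the main relations of the study", but Task 3.6 does not say whether they enter the regression.

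**The concern.** There are two separate gaps.

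The first is the model. Binary logistic regression needs a two-class outcome. If a numeric score is the outcome, it must be cut at a point that the plan does not give. Cutting discards information, and a cut chosen after the data are seen leaves the result open to selection. This regression is the only planned analysis that links the two halves of the WP3 objective, gut composition and clinical symptoms.

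The second is the number of tests. A taxonomic profile can supply tens of variables. If each is tested between arms at 0.05, some will look like probiotic effects by chance, and nothing in the plan would separate these from real shifts.

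**Working it through.** **1. The plan's own figure.** The plan gives no power or error figure for the microbiota analyses. Its only calculation is for MMSE in Task 3.1: SD 1.3, difference 1.1, alpha 0.05 (two-sided assumed), power 80%.

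n per arm = 2 × (1.96 + 0.84)² × (1.3/1.1)² ≈ 21.9, so 22. The t-based version gives 22.9, so 23. The plan states 25, which is within two patients of the t-based figure. This confirms that MMSE is handled as numeric. With 25 or 30 per arm, the associations rest on 50 or 60 patients.

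**2. Power if a numeric score is the outcome and is cut.** The documents give no correlations, so r = 0.3, 0.4 and 0.5 are assumed. For the uncut score with one taxon, power ≈ Φ(atanh(r) × √(n − 3) − 1.96). At n = 50:

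- r = 0.3: 0.310 × 6.856 − 1.96 = 0.16, power 56%
- r = 0.4: 0.424 × 6.856 − 1.96 = 0.94, power 83%
- r = 0.5: 0.549 × 6.856 − 1.96 = 1.81, power 96%

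Simulation with normal data, a median split and a likelihood-ratio test (4,000 runs per cell) gives, for r = 0.3/0.4/0.5:

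| n | Linear, score uncut | Binary logistic, score cut |
|---|---|---|
| 50 | 56/83/97% | 40/65/86% |
| 60 | 66/90/99% | 48/74/91% |

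Repeat runs at n = 50 centre on 57/83/97% and 41/65/86%. Null rejection was 4.0-5.3% for linear and 5.1-6.2% for logistic, so the gap is lost power. The same formula at n = 32 (√29 = 5.385) gives 38/63/84%, so a median split costs about as much as losing 18 of the 50 patients.

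**3. Where the loss is small or absent.**

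- *Staged scales left uncut.* Proportional-odds regression on five equal levels at n = 50 gives 53/82/95%.
- *Scores as predictors.* If a categorical microbiota variable is the outcome, the scores enter uncut and this loss does not arise.
- *Skewed, zero-heavy taxa, untransformed.* With an assumed log-SD of 1.5 and 30% zeros, linear power is 34/54/76% and logistic 33/52/70%. The gap is 1/2/6 points in these runs and about 2 to 5 points in a repeat. Logistic null rejection was 7%, so its power is slightly flattered. With log-SD 1.0 and no zeros, the figures are 46/67/88% and 38/58/77%.

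In the zero-heavy case the linear model itself loses 56 − 34 = 22, 83 − 54 = 29 and 97 − 76 = 21 points. Leaving such taxa raw therefore costs more than the choice of model.

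**4. Effect of adjusting for arm.** Assume the probiotic shifts the taxon by 1.5 SD and the taxon drives the score with slope 0.3 or 0.4. At n = 50, power is 72/92% without arm in the model and 52/76% with it. With a 0.8 SD shift it is 60/83% and 53/76%.

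**5. Multiplicity in the arm comparison.** The number of taxa m is assumed. Expected chance findings = 0.05 × m. The chance of at least one is 1 − 0.95^m if taxa are independent. For correlated taxa (0.3), null t-tests with 25 per arm were simulated.

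| m | Expected | Any, independent | Any, correlated 0.3 |
|---|---|---|---|
| 5 | 0.25 | 23% | 21% |
| 10 | 0.5 | 40% | 35-36% |
| 20 | 1 | 64% | 53-54% |
| 50 | 2.5 | 92% | 80-82% |
| 100 | 5 | 99.4% | 94-95% |

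Testing both visits doubles the expected count. With taxa correlated 0.3 and a within-taxon visit correlation of 0.6 (assumed), the chance of any is 54/75/95/99% for 10/20/50/100 taxa. Benjamini-Hochberg control at 5% brings it to about 4-6%, for one visit or pooled over both.

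**The case against.** The strongest reply is that both harms depend on choices the plan has not made. It does not say that scores will be the outcome or will be cut, and naming a chi-square test shows that some categorical data are expected. It does not say that taxa will be tested one by one. A methodology specialist is to review the analysis and may add to it. All of this is correct, and it makes both harms conditional. It does not close the gap: a decision taken at the time of analysis is not a rule fixed in advance, and further analyses could enlarge the set of tests.

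It is also fair that the size of the power loss depends on the shape of the taxon data, and that routine adjustment for arm could weaken the very link the model is meant to show. Both points stand and shape the fix.

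A reader might infer that chance taxa will be passed to the public as probiotic benefits, because WP4 plans to "educate of the benefits of the variables studied and resulted positive, e.g. the Mediterranean lifestyle, probiotic consumption etc". The document does not support that. Its examples are lifestyle and probiotic consumption, and no public advice on single taxa is planned.

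**Conclusion.** The concern holds in conditional form. Task 3.6 leaves the association model undefined and puts no control on the microbiota comparisons, and nothing elsewhere in the document supplies either.

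If numeric scores are cut, the loss at n = 50 is about 57 − 41 = 16, 83 − 65 = 18 and 97 − 86 = 11 points for r = 0.3/0.4/0.5. This rests on a median split, one predictor, and normal or suitably transformed taxa. If 20 to 100 taxa are tested singly at one visit, at least one chance finding has a probability of 53% to 99%, depending on their number and correlation. Correlation between taxa lowers that probability but not the expected count.

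Two stronger readings are tempting and do not hold. One is that logistic regression as such wastes power; the loss comes from cutting a numeric score. The other is that the trial's main comparison is compromised. MMSE is compared between arms by a method that needs no cut, so the choice of logistic regression does not affect it. The point is worth correcting before analysis but does not threaten the sizing of the trial.

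**What to change.** In Task 3.6:

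1. Replace the logistic sentence with linear regression for numeric scores and ordinal regression for GDS-FAST and CDR, with the score as outcome and adjustment for its baseline value. Name any other covariates, including whether the lifestyle and life-events questionnaires enter.
2. Require taxon abundances to be transformed before modelling, for example by log-ratio or rank.
3. Keep binary logistic regression only for an outcome whose cut-point is written down before data are seen.
4. Report each association with and without adjustment for arm. Adjustment guards against confounding by arm, but can remove part of the path from probiotic to taxon to score.
5. Fix the taxonomic level, the microbiota measures and the visits to be tested before sequencing data arrive.
6. Apply Benjamini-Hochberg false discovery rate control (5% in the examples below) to two families: taxon-level arm comparisons and taxon-score associations. Label the association models exploratory.

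No new data are needed, only wording and a little more analysis. The real price is fewer true findings in both families. Assumed examples with independent tests:

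- *Arm comparison, 25 per arm, 20 taxa, 4 truly shifted by 0.8 SD:* true findings fall from 3.2 to 2.0, false ones from 0.81 to 0.12.
- *Arm comparison, 50 taxa, 5 shifted by 0.8 SD:* true findings fall from 4.0 to 1.9, false ones from 2.2 to 0.13.
- *Associations, n = 50, 20 taxa × 10 scores = 200 tests, 10 true at r = 0.4:* true findings fall from about 8.3 to 3.5, false ones from 9.2 to 0.2.

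A short list fixed in advance, such as about five summary measures, would leave much less multiplicity to control.
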